### 4.4 Data Analysis

#### Phase I

The purpose of Phase I is to evaluate the feasibility of the self-guided Limbix Spark program. Feasibility outcome measures for conducting an RWE fully remote trial of a novel digital treatment for adolescent depression will include enrollment feasibility (i.e., proportion of recruited participants ineligible to participate and/or who decline to enroll), intervention tolerability (i.e., proportion of enrolled participants who discontinue intervention, are lost to follow-up, or experience clinical concerns), and adherence (i.e., proportion of modules completed). Self-report assessments will be collected at pre and post program time points. Weekly PHQ-8 assessments will also be collected during the 5-week intervention as well as at pre and post time points.

Self-reports of clinical concerns will be collected weekly from both the participant and legal guardian (where required) during the 5-week intervention. Patient feedback on ease of use, satisfaction with technology and content, expressed willingness to continue use, and enjoyment will be assessed via questionnaires and a qualitative interview following the intervention. Adherence will be tracked via the mobile app, which will log the time and duration of sessions and user activities.

As per recommendations for pilot studies, formal hypothesis testing will not be prioritized in data analysis. The sample size and planned data analysis, which will rely on qualitative and confidence interval approaches, are appropriate to accomplish the stated objectives of this trial phase. Confidence intervals will be calculated for each outcome measure using varying levels of confidence to evaluate preliminary evidence of effectiveness and feasibility. Feasibility and acceptability of the intervention will also be qualitatively evaluated based on post-intervention interviews with patients. Post-intervention participant interviews are expected to demonstrate that the intervention was feasible for participants to integrate into their daily routine, easy to use, and deemed acceptable and efficacious for helping participants live well with their depression symptoms.

Means, variability, and effect sizes for primary and secondary outcomes will be calculated. A confidence interval approach, using multiple levels of confidence to evaluate the strength of preliminary evidence of efficacy measured by the PHQ-8, will be taken to evaluate whether the mean treatment difference is above zero and whether confidence intervals include a clinically important difference for outcomes. Clinical significance for changes in depressive symptoms will be considered a 5-point reduction in PHQ-8 scores and a post-intervention PHQ-8 score of  $\leq 9$ . For all other measures, clinical significance will be defined as a standardized effect size between 0.3 and 0.5. The time course of weekly PHQ-8 scores will be plotted to assess trends in change over time.

Lastly, we will assess treatment adherence and usability by evaluating program completion and daily mobile app usage, and evaluating means and variability in self-reported usability and engagement using the SUS and UES in the treatment group.

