## **2. Criteria for Subject Selection**

### **2.1 Number of Subjects**

A convenience sample of participants will be recruited via online advertising, social media, word of mouth, flyering, and recommendations by doctors, schools, and other youth and/or health-focused organizations. Limbix may also work with participant recruitment companies, such as TrialFacts and Dynata. Healthcare providers involved in identifying potential study participants may be compensated for recruitment efforts (based on hourly effort and not on number of referrals or enrolled participants). A total of 60 participants will be recruited in Phase I, and a minimum of 120 participants with PHQ-8  $\geq 10$  will be recruited in Phase II. A statistically powered Phase III study will be designed following completion of Phase II.

Preliminary power calculations revealed that a sample size of 175 will achieve 80% power to detect a moderate effect size (Cohen's  $d=0.5$ ) between Limbix Spark and active control at a significance level of 0.05 for a two-tailed t-test with an estimated 27% attrition rate. A moderate effect size is expected based on previous digital interventions with active controls for depression and evidence of superior efficacy for CBT-based interventions. An effect size will be calculated at the end of Phase II and may inform power calculations in determining sample size for Phase III.

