There will be two phases of this study. Phase I will evaluate feasibility of a minimum viable product (MVP) version of the Limbix Spark mobile app (Version 1) within the context of a real world deployment. After feasibility is established, Phase II will be initiated during which a primary outcome of effectiveness of the Limbix Spark app will be evaluated. At the commencement of Phase II, an updated version of Spark (Version 2) will be implemented. In order to quickly support teens during COVID-19 with an engaging and efficacious digital treatment, one additional app update is planned (Version 3) during Phase II. Recruitment for Phases I and II may not be powered to detect statistically significant differences between Spark and the educational control condition. Participants in Phase I will be randomized using a 1:1 ratio. Participants in Phase II will be randomized using a block randomization approach to ensure equal group sizes. Block size will range in multiples of 2 from 4-12 and be randomly generated to prevent guessing of allocation and eliminate bias.

In Phase I if the participant does not complete the post-intervention assessments within 4 weeks from the end of the intervention period they will be considered lost to follow up. If a participant chooses to withdraw from the study at any point or is deemed lost to follow up or dropped from the study during the intervention period (5 weeks), access to the web portal and mobile app will be restricted at that time. Otherwise, access to the mobile app will be restricted at the end of the 5-week intervention period and access to the web portal will be restricted after post-intervention assessments have been completed or the participant is deemed lost to follow up (4 weeks after intervention period). Participants will be compensated \$25 in the form of an electronic gift card or cash transfer for completing the post-intervention assessments regardless of adherence to their assigned intervention. Gift cards will be emailed to participants.

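### On the Phase I secondary scales, an interval that includes an effect of 0.3 to 0.5 SD says little about benefit, and very large effects fail the criterion

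*Combined protocol and SAP*

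**What the plan says.** Section 2.1 sets the size of the phase: "A total of 60 participants will be recruited in Phase I". Section 3.1 sets the allocation: "Participants in Phase I will be randomized using a 1:1 ratio".

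Section 4.4, Phase I, makes the phase a feasibility study in which hypothesis tests are not the priority. Intervals carry the efficacy information instead: "Confidence intervals will be calculated for each outcome measure using varying levels of confidence to evaluate preliminary evidence of effectiveness and feasibility". The levels are not named. The next paragraph takes up the strength of preliminary evidence on the PHQ-8 and asks two things of the intervals: "whether the mean treatment difference is above zero and whether confidence intervals include a clinically important difference for outcomes".

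For the PHQ-8, the important difference is a 5-point fall together with a final score of 9 or less. For the rest: "For all other measures, clinical significance will be defined as a standardized effect size between 0.3 and 0.5". In Section 4.2 the other clinical scales are GAD-7, the PROMIS child and parent-proxy scales, and the MFQ.

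The section does not say how the two questions combine, or whether inclusion counts for the app or only leaves the matter open.

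**The concern.** An interval includes a target when it is wide enough and roughly in the right place. In a small trial, width does most of the work, so inclusion can reflect imprecision rather than benefit.

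The closed range adds a second fault. A benefit large enough to put the whole interval above 0.5 SD no longer includes the target, and an effect of 0.8 SD, taken literally, is not clinically significant at all.

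Using several confidence levels does not help, because the higher the level, the wider the interval and the more easily a useless app meets the criterion. At stake is how Phase I results on the secondary scales are described: null results could be presented as encouraging and very strong ones as falling outside the criterion.

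**Working it through.** **The plan's own calculation.** The only sample-size figure is "a sample size of 175 will achieve 80% power to detect a moderate effect size" (Cohen's d = 0.5), "at a significance level of 0.05 for a two-tailed t-test", "with an estimated 27% attrition rate". The exact t-test needs 63.77 per arm, and 2 × 63.77 / 0.73 = 174.7, so 175 reproduces. It does not cover Phase I, whose 60 has no power or precision basis.

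**Inputs.** 60 participants at 1:1 gives n = 30 per arm. As an assumption, carrying the 27% attrition over to Phase I leaves 30 × 0.73 ≈ 22 per arm. Outcomes are taken as normal with equal variances and coded so that a positive difference favours Spark. Effects are in SD units.

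**Interval width.** SE = √(2/n) = √(2/30) = 0.258. The 95% half-width is 2.002 × 0.258 = 0.517. At n = 22 it is 2.018 × 0.302 = 0.608.

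**What inclusion requires.** The interval overlaps 0.3 to 0.5 when the estimate lies between 0.3 − 0.517 = −0.217 and 0.5 + 0.517 = 1.017. So an estimate of −0.2 (interval −0.72 to 0.32) meets it, and an estimate of +1.1 (0.58 to 1.62) does not.

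**Probability of inclusion**, Φ((1.017 − d)/0.258) − Φ((−0.217 − d)/0.258):
- d = 0: Φ(3.94) − Φ(−0.84) = 0.80
- d = 0.5: Φ(2.00) − Φ(−2.78) = 0.97
- d = 1.0: Φ(0.07) − Φ(−4.71) = 0.53

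**Whole interval above zero.** The estimate must exceed 0.517. At d = 1.0 this has probability 1 − Φ(−1.87) = 0.97. Adding inclusion confines the estimate to 0.517–1.017: 0.526 − 0.031 = 0.495.

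Simulation with estimated SDs agrees (30 per arm, 95%):

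| True effect (SD) | Inclusion alone | Mean > 0 and inclusion | Interval > 0 alone | Interval > 0 and inclusion |
|---|---|---|---|---|
| 0 | 79–80% | 50% | 2.5% | 2.5% |
| 0.5 | 97% | 95% | 48% | 45% |
| 0.8 | 79% | 79% | 86% | 65–66% |
| 1.0 | 52% | 52% | 97% | 49% |
| 1.2 | 24% | 24% | >99% | 24% |

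**Other settings.** At 22 per arm, inclusion alone is 84% at no effect and 62–63% at 1.0 SD. With 30 per arm and no effect it is 69–70% at the 90% level, 55% at 80% and 50% at 75%. At 1.0 SD the same levels give 39–40%, 26–27% and 22%. Parent scales are completed only for participants under 18 (Section 3.4), so they rest on fewer people; with an illustrative 15 per arm, a useless app meets inclusion in about 88% of trials.

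**PHQ-8.** No SD is given, so 4 to 7 points is assumed, with 5 points applied as a between-arm difference. Under no effect the 95% interval contains 5 in 0.3%, 3%, 11% and 22% of trials (SD 4, 5, 6, 7; 30 per arm), or 2%, 10%, 23% and 36% (22 per arm). At a true 5 points it is 95%. Inclusion falls back to the null rate only near a 10-point difference.

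**Comparison rule.** With 30 per arm, a lower limit above zero occurs under no effect in 2.5% of trials (95% level) or 10% (80% level). At 0.5 SD the figures are 48% and 74%; at 1.0 SD, 97% and over 99%.

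**The case against.** Four stronger readings are tempting, and the documents do not support them.

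- **That Phase I would declare most useless apps effective.** The plan evaluates whether the two conditions hold; it sets no pass/fail rule. It also asks about zero, and in a confidence-interval approach the natural reading compares the interval with zero. The null rate is then 2.5%. Even the loosest reading, a positive point estimate plus inclusion, gives 50%.
- **That the main efficacy outcome is affected.** The sentence names the PHQ-8, and on its 5-point benchmark a useless app meets inclusion in roughly 0.3% to 36% of trials, depending on the assumed SD and number per arm.
- **That the criterion cannot tell a promising app from a useless one.** At 0.5 SD, the effect that Section 2.1 expects, inclusion alone rises from 80% to 97%, and with a positive mean from 50% to 95%. The reversal needs a true effect above about 0.8 SD.
- **That a wrong decision to proceed could follow.** Section 3.1 starts Phase II once feasibility is established, and the Phase I primary outcomes in Section 4.1 are feasibility measures.

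A further defence is that including the target may mean only that the upper limit reaches it. Then nothing reverses: at a threshold of 0.3 SD the rate goes from 79% at no effect to 100% at 1.0 SD. But that shows a benefit has not been ruled out, which is not evidence for one, and the text does not say this is what is meant.

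All of this narrows the point. What stands is that the interval approach applies to every outcome measure, its stated purpose is evidence of effectiveness, and the range for the other scales has an upper bound that serves no purpose.

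**Conclusion.** The point holds for the Phase I secondary scales (GAD-7, PROMIS, MFQ). Inclusion of 0.3 to 0.5 SD is met by about 80% of trials of a useless app with 30 per arm at 95%, and less often, about 52%, when the true effect is 1.0 SD. On the strict reading, where the interval must also exclude zero, inclusion gives no protection against false positives (2.5% with or without it) and loses about half of the successes at 1.0 SD (97% to 49%).

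These figures assume normal outcomes, equal variances and all 60 participants analysed; using 22 per arm does not change the conclusion. The result does not carry over to the PHQ-8 benchmark. The consequence is confined to how Phase I results are described, so this should be corrected but does not threaten the trial's main comparison.

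**What to change.** In Section 4.4, Phase I:

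1. For measures other than the PHQ-8, replace the closed range of 0.3 to 0.5 with a minimum: a standardized effect of at least 0.3.
2. Name the confidence levels in advance. State that preliminary evidence of benefit on an outcome means that the lower limit of the interval for the between-arm difference, coded so that positive favours Spark, exceeds zero, and report this at each named level. The choice of levels is the sponsor's; under no effect this happens in 2.5% of trials at 95% and 10% at 80%.
3. State that an interval reaching the important difference (0.3 SD for the other measures, the existing 5 points for the PHQ-8) means only that an important benefit has not been ruled out. An upper limit below that difference means such a benefit is unlikely. An interval that includes zero and also reaches the important difference is reported as inconclusive.

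The PHQ-8 benchmark stays as it is. The same intervals are computed from the same data, so the cost is wording only. The downside is that more Phase I outcomes will be reported as inconclusive.

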## Phase II

The main purpose of Phase II is to evaluate the effectiveness of the Limbix Spark program relative to an educational control condition. All analyses will be restricted to those participants with PHQ-8  $\geq 10$  unless otherwise indicated. Data from participants who reported a change in their medication or treatment for a mental health disorder that occurred during the study may be excluded from primary analysis. The core analysis strategy in this project is longitudinal mixed effects modeling, where we fully utilize the repeatedly measured primary and secondary outcomes and maximum likelihood estimation will be applied.

Data across versions 2 and 3 will be pooled and statistical analyses conducted with the combined dataset may be computed with version included as a covariate. Statistical analyses may also be conducted separately for versions 2 and 3 cohorts. All analyses will be completed in line with the intent-to-treat (ITT) principle, where all participants will be included in the analyses according to their assigned study arm at baseline, regardless of adherence to study protocol. Modern per protocol analyses will also be conducted to estimate treatment effects for participants who adhered to the protocol. All analysis results will be two-tailed, with a significance level at 0.05 and 95% confidence intervals.

All measures will be analyzed using mixed effects modeling, followed by generalized estimating equations to account for irregularly spaced measurements, fully utilizing all repeated measures and all available data. Missing data will be imputed using multiple imputation and likelihood-based analyses. Case analysis or single

imputation methods may also be used and a specific approach for imputation will be selected based on key attributes of the obtained data, including % missing and whether data are missing at random^109. Sensitivity analyses will be conducted to determine if data are missing at random. In these analyses, allowing for random intercepts and slopes, the change (slope) will be the key dependent variable and the randomization status will be the key independent variable. The results of these analyses can be easily converted to group or treatment differences at post assessments. In our mixed effects modeling, all variables will be analyzed as continuous with the exception of clinical concerns (occurrence/non-occurrence), which will be treated as a repeatedly measured binary outcome.

As an exploratory investigation, multiple variables will be investigated as possible moderators of treatment effects on depressive symptoms (PHQ-8). For example, we may evaluate medication status, symptom severity, age, sex, COVID19 specific factors, and aspects of program engagement (e.g., time to complete program, duration of use) as potential moderators. For this investigation, we will employ the MacArthur framework for moderator analysis, following the eligibility and analytical criteria for determining moderators. To maximize power, moderator analyses will also be conducted using mixed effects modeling.

Exploratory analyses using mixed effects modeling will also be conducted to evaluate whether successive program updates (between versions 2 and 3 of Limbix Spark) result in statistically significant differences on primary and secondary outcome measures, including depressive symptoms, global functioning, and treatment adherence, usability, and engagement.

Content analysis of post-study interviews will be conducted. Data will be codified to identify themes with an emphasis on engagement, usability, comprehension, therapeutic alliance, and overall impact of treatment. Key insights will be drawn from themes and contextualized with quantitative user session data.

Lastly, we will assess treatment adherence by evaluating treatment-related differences in rates of program completion and daily mobile app usage using independent samples (between treatment and control groups) or paired (within the educational control group) t-tests. We will also assess treatment-related differences in self-reported usability and engagement using the SUS and UES scales descriptively by comparing means and variability between groups and within group (control group only)

Statistical analyses for the primary outcome variable and between group differences in rates of clinical concerns rates will be conducted when N=60 (~30/grp) and N=120 (~60/grp) participants have completed Phase II. If no statistical differences are detected in the primary outcome variable, possible moderators of treatment status on the primary outcome may be evaluated, including age, concurrent treatment, and PHQ-8 score at baseline. Results of the interim analyses may be used to adjust recruitment targets for the remainder of the trial.

An effect size will be calculated for the primary outcome and may be used to determine sample size for a Phase III trial.

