Both mobile programs (Limbix Spark and educational control) will be fully self-guided, completed by participants at home. Each program is designed to be completed over 5 weeks but users may progress through the program at their own pace. The Limbix Spark program progresses linearly, i.e., a task must be completed before a participant can progress to the next task. Content for a given week is not expected to take more than 60 minutes to complete. All participants will be prompted to complete a weekly PHQ-8 and clinical concerns questionnaire in the mobile app. Automated app notification reminders to complete these questionnaires will be sent. If users have not opened the app in 3 days, an automated app notification encouraging participants to use the app will be sent. An automated reminder notification will be sent 7 days before the end of the intervention period to remind participants that the intervention period will be ending in 7 days.

The legal guardian of participants under 18 will be emailed links to complete a parent-reported participant symptom check weekly. If they have not completed the questionnaire, they will be sent a reminder email 6 days later to remind them that the questionnaire is due the next day.

After the 5 week intervention period, participants and their legal guardian (if required) will be emailed links to complete post-intervention self-report assessments via secure web portal. Participants and their legal guardian (if required) will receive automated email reminders to complete the post-intervention assessments after 6 days if they have not completed the assessments. If participants or their legal guardian do not complete the post-intervention assessments within a week the research coordinator may reach out to participants or legal guardians via phone or email to encourage them to complete these assessments.

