In Phase II, for participants randomized to the treatment arm, if the participant does not complete the post-intervention assessments within 2 weeks from the end of the intervention period they will be considered lost to follow up. If a participant chooses to withdraw from the study at any point or the participant is deemed lost to follow up or is dropped from the study during the intervention period (5 weeks), access to the web portal and mobile app will be restricted at that time, otherwise access to the mobile app will be restricted at the end of the intervention period and access to the web portal will be restricted after post-intervention assessments have been completed or the participant is deemed lost to follow up (2 weeks after intervention period).

Participants randomized to the control arm will have two weeks to complete the post-intervention assessments. Once the post-intervention assessments have been completed or 2 weeks have passed, whichever occurs first, participants in the control arm will be granted access to the treatment condition (Limbix Spark) for 5 weeks. After access to Limbix Spark for 5 weeks, participants will have two weeks to complete another set of post-intervention assessments. If a participant chooses to withdraw from the study or the participant is deemed lost to follow up during the control app intervention period or Limbix Spark app intervention period (5 weeks

each), access to the web portal and mobile app will be restricted at that time. Otherwise, access to the mobile app will be restricted at the end of each intervention period and access to the web portal will be restricted after the second set of post-intervention assessments have been completed or the participant is deemed lost to follow up (2 weeks after Limbix Spark intervention period).

In Phase II, if participants report a change in their treatment for a mental health disorder while enrolled in the study, they may be withdrawn from the study.

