In Phase II, all participants will be compensated \$25 in the form of an electronic gift card for completing the baseline assessments and \$25 for completing each set of post-intervention assessments regardless of adherence to intervention (1 set of post-intervention assessments will be completed if assigned to the treatment arm and 2 sets of post-intervention assessments will be completed if assigned to the control arm-- 1 after completing the control app and another after subsequently completing the Limbix Spark app.) Gift cards will be emailed to participants.

If participants indicated during the consent process that they would be interested in participating in a post-intervention feedback interview, a research coordinator may contact participants and their legal guardian (if under 18) to set up this interview to be conducted over video conferencing. Participants who were randomized to the control condition may be contacted to complete these interviews following completion of the control arm, prior to starting the treatment condition. Participants and their legal guardian will be asked, separately, to answer questions about their experience with the program and provide feedback that may help improve the product for future users. These interviews may be audio-recorded with permission. These interviews are expected to take 1 hour, and participants and parent/legal guardians who participate will be compensated \$25/hr. Reimbursement will be prorated for interviews lasting less than 1 hour. For participants randomized to the control arm in Phase II, this interview will occur after completion of the Limbix Spark intervention period.

All relevant FDA requirements for the conduct of clinical trials will be followed, including registration on [clinicaltrials.gov](http://clinicaltrials.gov).

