## Description of Assessments

- The **Patient Health Questionnaire (PHQ-8)** is an 8-item self-report measure for screening for depression and for establishing depression severity. The PHQ-8 has been demonstrated to have high sensitivity and specificity in both adolescents and young adults. Clinically significant improvement is defined as a reduction in assessment score  $\geq 5$ . Post-intervention scores  $< 10$  are defined as remission.
- **Baseline Questionnaire- Participant and Parent:** Contains demographic, clinical history questions, and questions related to the impact of COVID-19.
- The **Brief Resilience Scale** is a 6 item self-report measure for assessing the ability to “bounce back” or recover from stress. It has been shown to be reliable and to measure a unitary construct.
- **7 item Generalized Anxiety Disorder scale (GAD-7).** The GAD-7 is a brief 7-item assessment for generalized anxiety disorder with satisfactory sensitivity and specificity. We will evaluate changes in anxiety symptoms given the high comorbidity between anxiety and depression.

- **PROMIS Pediatric Global Health Scale and PROMIS Parent Proxy Global Health Scale:** The PROMIS Pediatric and Parent Proxy Global 7+2 are 9-item measures that produce essentially a unidimensional measure of global health perception/well-being.
- **Mood and Feelings Questionnaire Short Parent version (MFQ-PS).** The MFQ-PS consists of a series of 13 descriptive phrases regarding how the subject has been feeling or acting recently and is a screening tool for depression in children and young people.
- **Participant Symptom Check- Participant & Parent.** Assesses parent and participant reported clinical concerns, severity level, and relationship of the clinical concern to the intervention.
- **Post-Program Questionnaire- Participant and Parent.** Contains questions about changes in treatment and questions about COVID19
- **System Usability Scale (SUS).** Provides a “quick and dirty”, reliable tool for measuring the usability of systems. It consists of a 10 item questionnaire with five response options for respondents; from Strongly agree to Strongly disagree. The SUS has become an industry standard, with references in over 1300 articles and publications. It is a very easy scale to administer to participants, can be used on small sample sizes with reliable results, and is valid – it can effectively differentiate between usable and unusable systems.

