###### Phase II

- Between-subjects treatment-related change in depressive symptoms from baseline to 5-weeks as measured by PHQ-8 for those with baseline PHQ-8  $\geq 10$ .

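### The treatment-change exclusion has no cut-off at the 5-week endpoint, so only controls can lose a recorded primary outcome because of a later event

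*Combined protocol and SAP*

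**What the plan says.** **Outcome.** Section 4.1 defines the Phase II primary outcome as "Between-subjects treatment-related change in depressive symptoms from baseline to 5-weeks as measured by PHQ-8", in those with a baseline score of at least 10.

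**Exclusion.** Section 4.4 (Phase II) says: "Data from participants who reported a change in their medication or treatment for a mental health disorder that occurred during the study may be excluded". This applies to the primary analysis. The same section promises ITT analyses that include every participant as assigned.

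**Timeline (3.1 Procedure).** "Each program is designed to be completed over 5 weeks". In the Spark arm, "if the participant does not complete the post-intervention assessments within 2 weeks from the end of the intervention period" they count as lost to follow-up, and participation ends there. "Participants randomized to the control arm will have two weeks to complete the post-intervention assessments"; when that set is done or the two weeks have passed, whichever is sooner, "participants in the control arm will be granted access to the treatment condition (Limbix Spark) for 5 weeks". They then have two more weeks for another set. The payment paragraph confirms that "2 sets of post-intervention assessments will be completed if assigned to the control arm", against one set for Spark.

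**How changes are learned of.** Participants are asked at consent to tell the team about treatment changes. The Post-Program Questionnaire, which 3.4 schedules at post-intervention, "Contains questions about changes in treatment and questions about COVID19". The withdrawal rule in 3.1 runs for as long as the participant is enrolled, so it is equally open-ended.

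**The concern.** The analysis compares the arms at 5 weeks, but the exclusion follows each participant to the end of participation, and that point differs by arm. For Spark it coincides with the primary assessment. For control it comes after a further treatment period and a second round of questions about treatment changes.

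A treatment change after the week-5 score cannot have influenced that score, so removing the score has no scientific rationale. Because only controls can be removed in this way, the remaining groups are no longer those that randomisation made comparable. The effect size from this comparison may also be used to size Phase III (4.4).

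**Working it through.** **1. The plan's own duration.** Inclusion criterion 4 (2.5, Phase II) gives a study of up to 12 weeks. The windows in 3.1 sum as follows.
- Spark: 5 + 2 = 7 weeks at most.
- Control, first set done at once: 5 + 0 + 5 + 2 = 12 weeks.
- Control, both two-week windows used in full: 5 + 2 + 5 + 2 = 14 weeks.

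The stated 12 is reached only by leaving out one two-week window (5 + 2 + 5 also gives 12). The two figures should be reconciled, but the point holds with either.

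**2. Time at risk after the first assessment.**
- Spark: 0 weeks.
- Control assessed at week 5: 12 − 5 = 7 weeks at most.
- Control assessed at week 7: 14 − 7 = 7 weeks at most, or 12 − 7 = 5 weeks to the end of Spark access.

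**3. Share of controls exposed.** The weekly rate h is assumed to be 0.5-2%. With the first assessment at week a and the end at week b, the share of all controls whose first change falls after the first assessment is (1−h)^a − (1−h)^b.
- Low: 0.995^7 − 0.995^12 = 0.9655 − 0.9416 = 2.4%.
- High: 0.98^5 − 0.98^12 = 0.9039 − 0.7847 = 11.9%.

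Among controls with no earlier change, the share over k weeks is 1 − (1−h)^k: 1 − 0.995^5 = 2.5% and 1 − 0.98^7 = 13.2%. With about 60 per group (4.4), 2.4-11.9% is about 1 to 7 controls.

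**4. Shift in the control week-5 mean.** Assume a standard normal week-5 score and a logistic probability of exclusion, with an odds ratio of 1.5 to 3 per SD and the overall share p from step 3. The mean of those kept is the average of the score weighted by (1 − probability of exclusion).
- p = 2.4%: −0.010 SD (odds ratio 1.5) to −0.025 SD (odds ratio 3).
- p = 11.9%: −0.047 SD to −0.115 SD.
- p = 13.2%, odds ratio 3: −0.13 SD.

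The range is therefore about 0.01-0.12 SD, or 2-24% of the planned d = 0.5 (0.01/0.5 and 0.12/0.5). If the odds rise as scores fall, the size is the same and the sign reverses.

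**5. On the change score.** Exclusion removes the baseline too. With equal SDs and baseline-to-week-5 correlation r, the shift in change-score SDs is the step-4 shift × √((1−r)/2). The factor is 0.592 at an assumed r = 0.3 and 0.387 at r = 0.7. The range becomes 0.010 × 0.387 = 0.004 to 0.115 × 0.592 = 0.068.

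**6. With a common cut-off.** Both arms are at risk for at most 7 weeks, and the post-assessment exposure of controls falls from up to 7 weeks to 0.

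**The case against.** The strongest reply is that the exclusion is permissive and that the ITT statement beside it already keeps everyone in. If the ITT statement governs, the problem leaves the primary analysis. That is right as far as it goes, but 4.4 contains both statements and does not say which prevails. A discretionary exclusion that can be exercised after outcomes are known needs a stated window more than a fixed rule does.

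It can also be said that the sponsor meant the first five weeks. No section says so, and stating it would cost one sentence.

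Several stronger readings are tempting but not supported.
- A reader might infer that the rule works against Spark, because unwell controls seek new treatment. The rule covers any change. Removing controls who worsened would shrink the Spark effect; removing controls who improved and stopped treatment would inflate it. The documents do not settle which dominates.
- A reader might take 7 against 14 weeks as the excess exposure. That includes the shared first period. Weeks 6-7 can precede a late assessment in either arm, and exposure after a recorded first set is at most 7 weeks. A control who reaches week 14 either completed that set at week 7 or missed it, in which case there is no portal outcome to lose.
- A reader might infer that the per-protocol analysis inherits the flaw. Section 4.4 describes that analysis by adherence to the protocol and does not build it on this exclusion.

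The requirement of two months' stable treatment at entry also makes the higher assumed rates less certain.

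**Conclusion.** The gap is real. As written, the rule permits the removal of a control's recorded 5-week outcome because of an event up to 7 weeks later, and it permits nothing similar for Spark. This follows from the documents alone, taking the control arm's second set to repeat the Post-Program Questionnaire. The schedule in 3.4 has a single post-intervention column and makes no exception for that set.

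The consequence is possible, not certain, and its direction is unknown. Its size rests wholly on the assumed rates, odds ratios and correlations in the working. On these it runs from negligible to about 0.12 SD on the week-5 mean, and to about 0.07 SD on the change score. It would be zero if later changes were unrelated to the 5-week outcome. The point should be corrected because the rule is asymmetric and the remedy is cheap; no particular bias has been shown.

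**What to change.** In 4.4 (Phase II):

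1. State that the primary ITT analysis keeps all randomised participants with baseline PHQ-8 of at least 10, whatever treatment changes they report.
2. Wherever the treatment-change exclusion is still used, for example in a sensitivity analysis, close its window in both arms at the first post-intervention assessment, and no later than the end of that assessment's two-week window. Use only notifications received by then and the first Post-Program Questionnaire.
3. State that changes reported in the control arm's later Spark period bear only on the exploratory control-only analyses in 4.3.

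Setting the cut-off by source of report matters, because no section says that changes are dated. It needs no dates, and it gives each arm one questionnaire and the same notification period. The cost is a short addition to the text and slightly fewer exclusions. An early change that a control reports only in the second set would not count, but Spark participants have no second chance to report either. The change concerns analysis sets only and leaves the withdrawal rule in 3.1 untouched.
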